5. ONGOING GRANTEE AND LOCAL EVALUATOR COORDINATION

Describe how the grantee and local evaluator collaboratively worked together to identify the research question(s) and research design to ensure its feasibility and relevance. Describe how the grantee and local evaluator will continue to work together throughout the evaluation to proactively address unforeseen challenges as they arise and ensure the rigor and relevance of the evaluation and its findings. Describe how the grantee and local evaluator will coordinate dissemination efforts. Describe how these processes will occur while maintaining the independence of the evaluation.

Fathers Incorporated and the local evaluator, Midwest Evaluation and Research (MER) began the process of collaboration prior to the release of the Funding Opportunity Announcement (FOA) for this project. This included multiple working meetings to discuss the project and the goals that Fathers Incorporated had for the project, with a specific emphasis on what they had learned as a funded OFA grantee over the last two cohort cycles and what they would like to do differently. This included a discussion of enhancements to the program they believed would enhance participant outcomes, and the resource requirements of these enhancements. Several viable and relevant research question options were developed prior to the FOA and when the FOA was released the team had additional meetings to discuss the program that would be proposed to meet the goals and objectives of Fathers Incorporated and OFA and how well the research question alternatives developed in advance worked with this program outline. Using this extended collaborative process, the research questions were designed that were most relevant and feasible.

The basis for ongoing coordination between Fathers Incorporated and MER is regular communication. This will be accomplished by the way of bi-weekly meetings and daily interactions between staff. Fathers Incorporated and MER have established a set of standing calls and meetings which began in the first quarter of funding. This includes a bi-weekly (every other week) meeting of the CQI team. This is a team that is led by the CQI Data Manager and MER Lead Evaluator will discuss program implementation, data from the nFORM and local evaluation systems and closely examine trends and accomplishments (see CQI section for more detail on these meetings). This team includes Fathers Incorporated organizational and project leadership, the MER Evaluation team, and front-line staff in the form of Case Manager and Facilitator representatives.

In addition to this CQI team, a monthly meeting of program and organization leaders and MER staff will occur to ensure the partnership and coordination is on track and running smoothly. Regular contact allows close coordination. Perhaps the greatest asset to this coordination effort is the CQI Data Manager which is a shared and co-funded staff person that is embedded

with Fathers Incorporated staff and acts as staff for both MER and Fathers Incorporated - bridging the gap between the organizations.

This person will interact with program staff daily while completing the duties of a CQI Data Manager. These meetings and staffed position will continue during the entire project period and will include addressing opportunities for dissemination (shared efforts with project staff) and ensuring the rigor and relevance of the evaluation and its findings.

MER has operated prior RCT evaluations with this exact process, by clearly outlining roles and responsibilities – such as the evaluation team helps identify and illuminate areas of concern or improvement (for the program and the evaluation), but the program staff have responsibility for implementing program improvement and for providing direct services to participants.

Fathers Incorporated and MER share a responsibility for a well-executed project and evaluation, but MER is also an independent and external organization that has high integrity and is not responsible in the outcomes of the program. This allows for a high level of coordination without allowing any co-dependence or for personal interests to influence evaluation findings. This was well demonstrated in MER's last evaluation which found the program enhancements being studied ineffective in improving outcomes.

7. SAMPLE

7.1. TARGET POPULATION(S)

For each target population identified in Section 1.2, please describe the target population(s), and explicitly state whether the population(s) differs from those who will be broadly served by the grant. Describe how the target population will be identified. Explicitly state the unit of analysis (e.g., non-residential father, unmarried couple).

Description of Target Population	How is the population different from those who will be broadly served by the grant?	How will the target population be identified?	Unit of Analysis
Urban fathers age 18 years and older with children who are up to 24 years of age	No difference, all program participants will be study participants	The sample will be identified and recruited by the program staff.	Urban fathers

7.2. METHODS TO PROMOTE SUFFICIENT PROGRAM PARTICIPATION

Please describe methods to promote sufficient program participation in the table below.

8. DATA COLLECTION

8.1. CONSTRUCTS AND MEASURES

Clearly articulate the constructs of interest, measures to evaluate those constructs, and specific data collection instruments. Provide any information on the reliability and validity of the data collection instruments. For standardized instruments, you may provide the citation for the instrument.

Construct	Measure	Instrument	Reliability and Validity (if standardized instrument, you provide a citation for the instrument)
Parenting Attitudes	7 items: frequency of key attitudes (categories, 5-point scale)	nFORM Community-Based Fathers Survey (A3: a-g)	nFORM
Parenting Behavior	1 item: hours spent w/ children in last 30 days (interval); 1 item: frequency reach out to children (categories, 5 point scale); 7 items: frequency engage in key behaviors (categories, 5-point scale)	nFORM Community-Based Fathers Survey (A2b, A2c, A5b: b-d, f-i)	nFORM
Co-Parenting Behavior	11 items: frequency of agreement with key co-parenting behaviors (interval, 5-point scale)	nFORM Community-Based Fathers Survey (A13: a-k)	nFORM, OLLE
Healthy Partner Behavior	1 item: feelings of being overwhelmed as parent (categories, 4 point scale)	nFORM Community-Based Fathers Survey (B3 – B3a)	nFORM

* you may add rows by hitting the tab button, or right click and select insert row below

8.2. CONSENT

Describe how and when program applicants will be informed of the study and will have the option of agreeing (i.e., consenting to) or declining to participate in the study.

Fathers Incorporated staff will make initial contact with interested applicants. They will describe the study and answer any questions at that time. If the applicant is interested in the project, he will be invited to an enrollment session where the consent form will be presented. Fathers Incorporated staff will ensure that the applicant understands the consent form, remind them that participation is voluntary, and that they can drop out of the project at any time for any reason without consequences. Informed consent will take place prior to program enrollment and the collection of evaluation data.

8.3. METHODS OF DATA COLLECTION

If the evaluation will collect multiple waves of data, describe the timing of these waves below. When describing follow-up periods, specify whether the follow-up period will be post-baseline, post-random assignment, or post-program completion.

Wave of Data Collection (e.g., baseline, short-term follow-up, long-term follow-up)	Timing of Data Collection
Baseline	Collected Immediately Following informed consent and enrollment – during and orientation session or first workshop.
Post-Test	Collected after the completion of core curriculum programing -during the last workshop session – approximately 13 weeks after enrollment.
1 year Follow-up (post-baseline)	Collected approximately one year after program enrollment/ baseline

For each measure, describe how data will be collected detailing which data collection measures will be collected by which persons, and at what point in the programming or at what follow-up point.

Measure	Timing of Data Collection (baseline, wave of data collection)	Method of Data Collection	Who Is Responsible for Data Collection?	Administrative Data Only: Will data access require data sharing agreement?
On Line Local Evaluation (OLLE) Baseline Survey	Baseline	Participant Self-Entered survey using online data collection program	Data Manager will proctor data collection and assist participants as necessary	No
OLLE Post-Test Survey	Post-Test (approx. 13 weeks after enrollment)	Participant Self-Entered survey using online data collection program	Data Manager will proctor data collection and assist participants as necessary	No
OLLE 1 Year Follow-up Survey	1 year after enrollment / baseline	Participant Self-Entered survey using online data collection program and link – or – Phone Interview data collection	MER Research Staff/ participant tracking team	No

* you may add rows by hitting the tab button, or right click and select insert row below

8.4. ENSURING AND MONITORING DATA COLLECTION

Describe plans for training data collectors and for updating or retraining data collectors about procedures. Detail plans to regularly review data that have been submitted and to assess and swiftly address problems.

This evaluation will utilize both post-program surveys (completed at the completion of core programming) and follow-up surveys collected one year after enrollment / baseline. The methods for these data collections differ. The primary driver for post-program survey completion is high rates of program retention. This data point will be collected during the last workshop session – after (but during the same session of) the completion of the nFORM post-program data collection. As such only those individuals who complete the program and who are at the data collection session will participate in the post-program data collection.

All program staff and evaluation staff will undergo a rigorous set of trainings to prepare for the evaluation. All staff receive an overview and introductory training to present the goals and objectives of the evaluation effort and its importance to the overall project. Next all staff receive training on human subject's protection and are required to pass a certification test on the subject matter. All staff will also receive a detailed training on the details of the evaluation including the evaluation tools, timing and data collection process.

In addition, the data manager and the primary local evaluation staff will undergo a rigorous training process to better understand the context of HMRF research, training on data collection procedures they will be responsible for, and training on the nFORM system and use of nFORM data in a CQI process. MER is creating networks of CQI data managers and Evaluation Project Managers across the 12 projects that we are evaluating so that all staff have access to experienced data managers and evaluation staff who have done this work previously. This training takes the form of weekly training sessions that are currently under way.

Members of the CQI team will also receive specific training on the MER CQI process that has been developed prior to the launch of data collection or program services. As described elsewhere MER is assisting the program staff in implementing a robust CQI process that will focus on retention as one of the primary areas of program improvement and as such we are anticipating relatively modest levels of attrition for this data collection.

On a bi-weekly basis the data manager, the local evaluation staff and MER technical specialists will be responsible for downloading data from the nFORM and MER On-Line Local Evaluation (OLLE) systems for processing and presentation to the CQI team for tracking and monitoring performance measurement outcomes (recruitment, enrollment, dosage, completion, referrals, etc.) so that near real time adjustments can be made to program implementation to ensure compliance with program goals and objectives.

All MER training is currently being recorded and as new staff come on board with projects or project staff turn over (or need refresher training) recorded training material can be shared and accessed with follow-up one on one training with the primary local evaluator and the MER LOB Lead, who has more than 15 years' experience in evaluating HMRF projects.

9. IRB/PROTECTION OF HUMAN SUBJECTS

Please describe the process for protection of human subjects, and IRB review and approval of the proposed program and evaluation plans. Name the specific IRB to which you expect to apply.

Because the planned evaluation involves human subjects, FI understands that program implementation requires both IRB approval and participant informed consent. MER has an established relationship with Solutions IRB. MER has had several research studies approved by Solutions IRB, and has submitted timely amendments when changes to studies needed to take effect. Solutions IRB, a private commercial Association for the Accreditation of Human Research Protection Programs Inc. (AAHRPP) fully accredited Institutional Review Board, will ensure that this study is approved before any research activities take place.

All submissions are completed online, so turnaround for a new study approval is between 24 to 72 hours, though the full approval process can take approximately one to two weeks depending on the number of questions and requested revisions that the IRB makes. In the IRB application submission, we will include descriptions of project staff, locations of study sites, the funding source, incentives, summary of activities, participant population, recruitment plans, risks and benefits, confidentiality of data, and the informed consent process along with all materials to be used in the study such as participant forms and surveys.

This project will be submitted for IRB approval in early March during the planning period in order to receive official approval to begin enrollment and data collection beginning in April.

Program staff and facilitators will also obtain Human Subjects Training Certification through the IRB to ensure the protection of participants.

10. DATA

10.1. DATABASES

For each database used to enter data, please describe the database into which data will be entered (i.e., nFORM and/or other databases), including both performance measure data you plan to use in your local evaluation and any additional local evaluation data. Describe the process for data entry (i.e., who will enter the data into the database).

Database Name	Data Entered	Process for Data Entry
nFORM	Performance Measurement Data	Entered directly by participants, and by program staff
Qualtrics	Local evaluation data, participant outcomes (OLLE survey)	Entered directly by participants, and by MER evaluation staff

* you may add rows by hitting the tab button, or right click and select insert row below

10.2. DATA REPORTING AND TRANSFER

For each database provided in the table above, please indicate the ability to export individual-level reports to an Excel or comma-delimited format and whether identifying information is available for linking to data from other sources.

Database Name	Ability to Export Individual Reports?	What identifying information is available to facilitate linking to other data sources?
nFORM	Yes	Client ID, name, DOB
Qualtrics	Yes	Client ID, name, DOB

* you may add rows by hitting the tab button, or right click and select insert row below

10.3. CURRENT SECURITY AND CONFIDENTIALITY STANDARDS

For each database provided in Section 11.1, please Indicate the ability to be able to encrypt data access during transit (for example, accessed through an HTTPS connection); be able to encrypt data at rest (that is, when not in transit), have in place a data backup and recovery plan; require all users to have logins and passwords to access the data they are authorized to view; and have current anti-virus software installed to detect and address malware, such as viruses and worms.

Database Name	Ability to encrypt data during transit?	Ability to encrypt at rest?	Data Backup and Recovery Plan?	Require all users to have logins and passwords?	Current Anti-Virus Software Installed?
nFORM	Yes	Yes	Yes	Yes	Yes
Qualtrics	Yes	Yes	Yes	Yes	Yes

* you may add rows by hitting the tab button, or right click and select insert row below

Please describe any plans for study registration with an appropriate registry (e.g., clinicaltrials.gov, socialscienceregistry.org, osf.io, etc.).

This study will be registered with clinicaltrials.gov.

Gentle Warriors Academy Healthy Marriage and Responsible Fatherhood Program Evaluation

4/22/2024

Clinicaltrials.gov ID: NCT06899100

Statistical Analysis Plan

1. Data Analysis

Briefly describe the planned approach for data analysis. If an impact analysis is proposed, name the key dependent and independent variables, and describe any methods to minimize Type I error (i.e., finding positive impacts by chance) such as limiting the number of impacts to be analyzed and/or multiple comparison correction. Describe proposed approach(es) for addressing missing data.

Analytic Sample

The study sample includes participants who: 1) gave recorded informed consent to be part of the study, and 2) took both an entrance and exit survey. The analytic sample for particular outcome measure will vary based on missing data.

Outcome measures

For each outcome construct, we have identified the relevant measures from nFORM and the OLLE survey that are theoretically aligned with that construct. We will generate a correlation matrix between items in a given construct to ensure that theoretically related items are also empirically related in our data set. Items that are not strongly correlated with other items in a construct will be removed as necessary. Factor analysis will be used to ensure that all construct items hang together (using an alpha of 0.7 or higher as the threshold).

Once we are confident that all of the items align with a given construct, we will create a composite measure by taking an average of the scores on each non-missing item in the construct. The measure definition matrix below provides information on each proposed outcome. For composite measures, a change score will be calculated between a participant's pre-program composite score and post-program follow-up composite score. For standalone survey items, a change score will be calculated between a participant's pre-survey and follow-up survey responses.

For the sake of consistency and simplicity, parenting and co-parenting analyses will use a participant's youngest child as the focal child.

Construct	Sample	Measure	Data source(s)	Variable Name
Parenting Attitudes (toward children)	Has at least one child age 24 or younger	7 items: frequency of key attitudes (categories, 5-point scale)	nFORM entrance, OLLE follow-up	Copar_Att

Parenting Behaviors (interaction with children)	Has at least one child age 24 or younger, saw child within past month	Continuous (1 item: hours spent w/children in last 30 days (interval); 1 item: frequency reach out to children (categories, 5-point scale); 7 items: frequency engage in key behaviors (categories, 5-point scale)	nFORM entrance, OLLE follow-up	Par_Beh
Co-parenting behavior	Has at least one child age 24 or younger, saw child within past month	11 items: frequency of agreement with key co-parenting behaviors (interval, 5-point scale)	nFORM entrance, OLLE follow-up	CoPar_Beh
Healthy Partner Behavior(Well-being as a parent)	Has at least one child age 24 or younger	1 item: feelings of being overwhelmed as parent (categories, 4 point scale)	nFORM entrance and exit	Well_being

Data preparation

We plan to clean each individual raw data file before merging nFORM and local evaluation surveys together for analysis in R using nFORM Client ID as the linking variable. Quality checks will include checks for duplicate surveys, incorrectly entered nFORM IDs, missing data, and outliers. We will look at descriptive statistics for our variables of interest to look for missing and outlying data.

Approaches to address missing data

Outcomes

When creating the composite measures for co-parenting and parenting relationships, we will create a composite score by taking the average of multiple individual items. For these measures, our current plan is to use 20% as a threshold for allowable missing items, based on guidance from evaluation technical assistance resources. This plan is contingent on the final distribution of missing data in our data set. With a 20% threshold, if a respondent is missing more than 1 item used for creating the co-parenting construct or more than 2 items for creating the parenting construct, the respondent will be assigned a missing value for that construct. We will not be imputing truly missing values for outcomes. To create a construct score, the average will divide by the number of non-missing values in the construct.

Participants who have not seen their child within the past month will have their parenting behavior responses set to “Never” (1) and will be included in the analytic sample for that outcome.

For outcomes that use single survey items, participants who do not respond to the item on either the pre- or follow-up survey will be excluded from the analytic sample for that outcome.

Assessing non-response bias

We will conduct response rate analysis for each primary outcome of interest to assess non-response bias and adjust for threats to internal validity. Using data from the Applicant Characteristics Survey, we will look at demographics (race, ethnicity, age, education level) and primary reason for joining the program among participants who fall into each of the following categories: 1) non-respondents who answered no surveys after the ACS, 2) respondents who completed the pre-survey only, 3) respondents who completed the post-survey only, and 4) respondents who completed both the pre- and follow-up survey (complete case).

Subgroup Analyses

We plan to compare data across two sets of subgroups. These are participants (fathers) whose ages range from 18-29 and those over the age of 30. We also plan to compare data across incarcerated participants and community participants.

Analytic approach

The main goal of this descriptive study is to assess pre-post change scores in the outcomes listed above among program participants before and after primary workshops. The changes will be assessed from program enrollment to one year after the enrollment (follow-up survey). We will use paired sample t-tests to assess the magnitude and significance of changes among program participants in the analytic sample for each outcome. We will adjust our p-values for multiple hypothesis testing and report the adjusted p-values in the appendix of the final report.

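### The SAP's sample rule requires an exit survey, but three of the four confirmatory outcomes are scored from entrance and one-year follow-up

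*SAP*

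**What the plan says.** **Sample rule.** SAP, Analytic Sample, admits fathers with recorded consent who "took both an entrance and exit survey". The sample may then differ between outcomes only through missing data. That can remove fathers, but it cannot restore one who has no exit survey.

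**Data sources.** The SAP's measure definition matrix takes parenting attitudes, parenting behaviors and co-parenting behavior from "nFORM entrance, OLLE follow-up". Only the well-being item, which stands for R4, comes from "nFORM entrance and exit". Exit and follow-up therefore appear in one table as different sources.

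**Time point.** Under Outcome measures, composite change ends at the "post-program follow-up composite score", and single-item change uses "pre-survey and follow-up survey responses". The Analytic approach runs change from enrollment to one year and calls that wave the follow-up survey. Protocol 1.2 labels R1 to R4 confirmatory and places each outcome one year after enrollment.

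**Waves.** Protocol 8.3 puts the post-test in the last workshop session, about 13 weeks after enrollment. The follow-up comes at about one year, by online link or phone. Protocol 8.4 places the nFORM post-program survey in that same last session, and limits post-program collection to fathers who both complete the program and attend that session.

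**Non-response.** The SAP plans a response analysis for each primary outcome with four groups: no survey after the applicant survey, pre-survey only, "respondents who completed the post-survey only", and a complete-case group defined by pre-survey plus follow-up.

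**The concern.** The sample rule names a survey that three confirmatory outcomes do not use. A father who missed the last workshop session but answered at one year has everything needed to score parenting attitudes, parenting behaviors and co-parenting. Taken at its word, the rule still excludes him. The non-response analysis would then place him among the complete cases, together with fathers who are analysed, so it could not show the exclusion.

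Two analysts could build different confirmatory samples from this SAP, and the choice could be made after results are seen. If fathers without an exit survey change differently from the rest, the two samples would also give different mean changes. Part of that difference would be a change of population rather than error.

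The well-being item has a related fault: its stated source is the exit survey, but the text on its time point says one year.

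**Working it through.** **Step 1: is there a figure to reproduce?** No. The documents give no sample size, exit rate or follow-up rate. The main check is therefore a comparison of the rules.

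**Step 2: fathers with an entrance survey, for the three outcomes scored at follow-up.** I take the nFORM exit survey to be the nFORM post-program survey of Protocol 8.4, and read the non-response groups per outcome, as the SAP states.

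| Exit | Follow-up | Meets sample rule | Can be scored | Non-response group |
|---|---|---|---|---|
| yes | yes | yes | yes | complete case |
| yes | no | yes | no | pre-survey only |
| no | yes | **no** | **yes** | **complete case** |
| no | no | no | no | pre-survey only |

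The third row is the contradiction: excluded by the rule, scorable by the matrix, and filed as a complete case.

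**Step 3: the well-being item.** The matrix gives "nFORM entrance and exit". Against that:
- The single-item change rule uses "pre-survey and follow-up survey responses".
- The single-item missing-data rule says "participants who do not respond to the item on either the pre- or follow-up survey will be excluded", and this is the only single-item outcome in the matrix.
- The Analytic approach and the R4 row of Protocol 1.2 both say one year.

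If the exit source is right, change is measured to about 13 weeks. If one year is right, the source entry is wrong and the sample-rule problem covers all four outcomes.

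**Step 4: illustration of size, literal reading only; every rate is assumed.** Let c be the share of entrance takers with an exit survey, and fc and fn the follow-up rates with and without one.

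Share of usable pairs dropped: d = (1 - c)·fn / [c·fc + (1 - c)·fn]. Standard error multiplier at equal SD: 1/√(1 - d).

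- c = 0.9, fc = 0.7, fn = 0.3: 0.03/0.66 = 4.5%; SE × 1.024.
- c = 0.8, fc = 0.6, fn = 0.4: 0.08/0.56 = 14.3%; SE × 1.080.
- c = 0.7: from 0.09/0.58 = 15.5% (fc = 0.7, fn = 0.3) to 0.12/0.54 = 22.2% (fc = 0.6, fn = 0.4).
- Wider assumptions: from 0.02/0.74 = 2.7% (c = 0.9, fc = 0.8, fn = 0.2) to 0.24/0.60 = 40% (c = 0.6, both follow-up rates 0.6).

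Protocol 8.4 expects fairly modest attrition at the post-program survey, which sits better with the first two lines, but it gives no number.

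**Step 5: if only completers are the target.** Let a be the share of completers without an exit survey and fa their follow-up rate: d = a·fa / [(1 - a)·fc + a·fa].

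- a = 0.05, fc = 0.7, fa = 0.4: 0.02/0.685 = 2.9%; SE × 1.015.
- a = 0.10, fa = fc: 10%; SE × 1.054.

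**The case against.** **Exit may be a loose label for the later survey.** Protocol 8.3 does not use exit as a wave name. The SAP's labels drift elsewhere: it writes "post-program follow-up composite score", and sets "respondents who completed the post-survey only" beside a complete case defined by follow-up. Protocol 1.1 and 4 speak of pre to post without dating the second measurement, while the dated statements point to one year. On this reading nobody is lost. The objection stands as a real possibility, and it makes the harm conditional. It does not settle the matter, because the matrix uses exit and follow-up as distinct sources.

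**A completer restriction may be intended.** R1 to R4 are worded for fathers who complete services (Protocol 1.1, 1.2 and Hypotheses). If so, excluding non-completers is correct. This also stands in part. But the SAP does not state the restriction, and exit-survey presence is a poor marker for it: by Protocol 8.4, a completer absent from the last session has no post-program survey.

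**Stronger readings that a reader might infer, and that the documents do not support:**
- That fathers with entrance and exit surveys but no follow-up fit none of the four non-response groups. The response analysis is planned per outcome, so for these three outcomes they are pre-survey only.
- That the matrix's Sample column shows no exit survey is required. That column names no survey at all, not even the entrance survey.
- That Protocol 7.1 makes all participants the analysis set. It compares the target population with those the grant serves, and the Evaluation Enrollment table already limits the study to those who consent.

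**Conclusion.** The contradiction is certain and lies within the SAP: the sample rule does not match the surveys that score three of the four confirmatory outcomes, nor the SAP's own complete-case definition. The consequence depends on the reading. Taken literally, scorable fathers are dropped and remain hidden among the complete cases. Taken loosely, the loss is zero.

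Neither size nor direction can be derived from the documents. The illustrative loss of about 4.5% to 14% of pairs (SE up about 2% to 8%), or about 3% to 10% if only completers count, rests wholly on assumed rates. A reader might infer that the rule inflates the estimated benefit, but nothing in the documents shows how fathers without an exit survey change.

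The well-being item's mismatch between source and time point is a separate fault. It needs repair whatever exit means in the sample rule.

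**What to change.** 1. For parenting attitudes, parenting behaviors and co-parenting, define the analytic sample as consent plus entrance survey plus one-year follow-up survey.
2. Reconcile the well-being item's source with its stated one-year time point, then set its sample by the two surveys that score it. First confirm whether the one-year survey carries the item, which the documents do not say.
3. Use the same survey pair and the same wave labels for each outcome in the non-response groups. A cross-tabulation of exit by follow-up is not needed once the rule is repaired.
4. If R1 to R4 are meant for completers, say so, define completion, and identify completers from the completion and dosage data already tracked (Protocol 8.4), not from exit-survey presence. Reporting an all-pairs estimate alongside is optional.

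The cost is a few sentences of SAP text. For the three OLLE outcomes no new data are needed: the SAP is dated 4/22/2024, and the Protocol's timeline runs follow-up collection to 8/15/2025. The downside is a possibly less favourable estimate if non-completers enter the analysis.
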